SAS	Simpson Angus Scale
Sheehan-STS	Sheehan Suicidality Tracking Scale
WOCBP	Women of childbearing potential

1 Trial 331-201-00182 COVID-19 Protocol Summary

1.1 Trial Design Schematic

^aStarting at Week 4, one dose decrease can occur at any time (scheduled or unscheduled visits) until the end of the trial. In addition, one dose increase can occur but only at the Week 6 scheduled visit. For subjects who may be offered entry into this trial as a result of early termination due to overwhelming efficacy from the 331-14-213 interim analysis, treatment in Trial 331-201-00182 will begin based on randomization and last visit completed in Trial 331-14-213. Subjects who received placebo in Trial 331-14-213 will receive active drug in Trial 331-201-00182. Subjects randomized to brexpiprazole and who completed the titration schedule in Trial 331-14-213 (ie, completed Week 4 visit in 331-14-213) will begin treatment on the same dose in this trial. Subjects randomized to brexpiprazole and who have not completed the titration schedule will restart drug in Trial 331-201-00182 dependent on the point in the titration scheme for Trial 331-14-213 that early termination occurred.

^bFor subjects who may be offered entry into this trial as a result of early termination of Trial 331-14-213 due to overwhelming efficacy from the interim analysis, the Screening/Baseline will occur at the last visit of the double-blind trial (ie, ET visit of Trial 331-14-213).

Figure 1.1-1 COVID-19 Impact Trial Design Schematic

^dAll subjects, whether they complete the trial or are withdrawn prematurely for any reason, will be followed up for a safety evaluation 30 (+ 2) days after the last dose of IMP during a clinic visit at either the investigator's site or residential facility, if applicable. If a clinic visit is not possible, the subject should be assessed by telephone contact with the subject and a caregiver.

^eFor all subjects who terminate early from the trial, all attempts will be made to collect mortality data by telephone contact with the subject's caregiver at Week 16 (relative to baseline visit).

^fAssessment is not obligatory if the visit is virtual.

^gIf the visit is performed virtually, the BARS and AIMS can be performed using videoconference. The SAS cannot be completed remotely.

^hFor the Weeks 1, 2 and 6 visits, if the visit is performed virtually, alternative methods for dispensing IMP to the subject can be performed, if allowed by country guidances and regulations, eg, use of courier or curbside pickup.

Protocol 331-201-00182

2 General Considerations

2.1 Telemedicine

All procedures and assessments in the protocol should be followed to the fullest extent possible. However, telemedicine can be used in cases where the site, subject and/or caregiver requests a virtual visit be performed due to COVID-19 conditions. Guidance will be provided to sites on whether use of phone is acceptable, or if video is required. Sites will be instructed to attempt to standardize collection via phone or video depending on the requirements of the trial to minimize confusion and risk of errors of utilizing varying collection strategies. All applicable country-by-country guidances and local regulations will be followed when implementing telemedicine options.

Note: If a trial-wide virtual visit mandate is declared due to COVID-19, virtual visit guidance is not applicable for hospitalized subjects where the investigator is also the subject's physician. Subjects who meet this description can continue in-person visits.

2.2 Reconsent

In cases where there is an immediate need to reconsent subjects and the subject and/or caregiver are unable to attend an in-clinic visit due to COVID-19 conditions, either paper reconsent or remote eConsent, in regions where remote capacity exists, are acceptable. Sites are to contact the clinical research organization (CRO) to discuss the options and agree to best approach for the site.

The investigator must continue to determine if there have been any changes to the prior assessment of the subject's capacity to provide informed consent. If changes have been made, refer to the instructions in the protocol ([Section 3.4.1.1](#)).

2.3 Protocol Deviations

Protocol deviations that occurred as a direct result of the COVID-19 pandemic and prior to a site's local regulatory agency and investigational review board/ethics committee (IRB/EC) approval of this addendum, must be recorded in eSource. A "direct result" is defined as being due to actual COVID-19 illness, or as a result of quarantine, social distancing, or site closures. The flexibility in procedures due to COVID-19 conditions allowed per this addendum (eg, virtual visits, missed assessments due to virtual visit, alternative investigational medicinal product [IMP] dispensation to subject), will not be considered protocol deviations following IRB/EC approval of this addendum. All other deviations will follow the normal deviation process described in the protocol and should not be entered proactively by sites.

Protocol 331-201-00182

2.4 Guidance to Record Adverse Events and Discontinuations Due to COVID-19

If a subject tests positive OR is presumed positive with COVID-19, the subject must be discontinued from the trial, and an adverse event (AE) of “Coronavirus Infection” OR “Coronavirus Positive Test Result” will be entered on the AE page of the eSource. A positive test result or a presumed positive subject is not automatically a serious adverse event (SAE), unless an SAE criterion is met (eg, hospitalization).

If a subject discontinues due to COVID-19 either because they test positive OR are presumed positive with COVID-19, then the primary reason for discontinuation should be reported as “Adverse Event” and indicate the AE number in the “Specify the reason for discontinuation” space that corresponds with the AE of “Coronavirus Infection” OR “Coronavirus Positive Test Result.”

If a subject discontinues due to COVID-19 for reasons other than the subject testing positive OR being presumed positive with COVID-19 (eg, quarantine, fear of infection), then the primary reason for discontinuation should be reported as “Other.” Be sure to specify the reason as “COVID-19” followed by the reason ensuring that the prefix of the description includes “COVID-19.” Do note that the reason “Other” should be selected even if the subject decides to withdraw consent or if the investigator decides to withdraw the subject due to COVID-19 concerns.

In case a caregiver is COVID-19 positive and another caregiver is available to continue the trial, the situation should be discussed with the medical monitor to determine continuation in the trial on a case-by-case basis. If there is no other caregiver, the subject needs to be early terminated from the trial.

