6.1 Subject Disposition, Completion Rate and Reasons for Discontinuation

Subject disposition will be summarized for the Enrolled Sample by parent study treatment group and overall.

Subject completion rate and reasons for discontinuation will be summarized for the Enrolled Sample by parent study treatment group and overall.

The above summaries will be repeated in subject subgroups as defined by gender (Female and Male), age group (< 65; \geq 65 and < 75; or \geq 75), race (white or other), geographical region (North America or other), and dementia severity (severe, moderate, and mild), where dementia severity will be defined based on Mini Mental State Examination (MMSE) score at baseline as follows:

- Severe: MMSE score \leq 12
- Moderate: MMSE score > 12 and \leq 18
- Mild: MMSE score > 18

SAP 331-201-00182

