9.1 Adverse Events

All adverse events will be coded by System Organ Class (SOC) and Preferred Term (PT) according to the Medical Dictionary for Regulatory Activities (MedDRA). AEs that are sex-specific, eg, ovarian cancer, will have their incidence rates evaluated for the specific sex.

Treatment-emergent AEs (TEAEs) are defined as AEs with an onset date on or after the first dose of IMP. In more detail, TEAEs are all adverse events which started after start of IMP; or if the event was continuous from baseline and was worsening, serious, study drug related, or resulted in death, discontinuation, interruption or reduction of study therapy. Adverse events occurring up to 30 days after the last day of IMP will be included in the summary tables.

The incidence of the following events in the open-label treatment phase will be tabulated by treatment group and overall using the Safety Sample:

- a) Treatment-emergent AEs (TEAEs)
- b) TEAEs by severity
- c) TEAEs potentially causally related to the IMP
- d) TEAEs with an outcome of death
- e) Serious TEAEs
- f) TEAEs leading to discontinuation of the IMP

The above summaries (b), (e) and (f) will also be prepared for TEAEs potentially causally related to the IMP.

In addition, incidence of TEAE during the open-label treatment phase of at least 5% by SOC and PT will be provided.

Incidence of TEAEs by SOC and PT will be summarized for sex, race, age and region subgroups.

Extrapyramidal symptoms (EPS)-related AEs will be grouped into five categories.

1) Dystonic Events, which include blepharospasm, cervical spasm, clumsiness, dystonia, dystonic tremor, emprosthotonus, essential tremor, facial spasm, fumbling, gait inability, head titubation, intention tremor, Meige's syndrome, muscle contractions involuntary, muscle spasms, muscle spasticity, muscle tightness, muscle tone disorder, musculoskeletal stiffness, myotonia, nuchal rigidity, oculogyration, oesophageal spasm, opisthotonus, opisthotonus, oromandibular dystonia, oropharyngeal spasm, pharyngeal dystonia, pleurothotonus, risus

SAP 331-201-00182

sardonicus, spasmodic dysphonia, tongue spasm, torticollis, torticollis psychogenic, trismus, uvular spasm;

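### Do COVID-19 withdrawals coded as adverse events distort the SAP's discontinuation tables?

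*Protocol*

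**What the plan says.** COVID-19 Addendum section 2.4 sets the rule: "If a subject tests positive OR is presumed positive with COVID-19, the subject must be discontinued from the trial". Footnote c of Addendum Table 1.2-1 repeats it. Neither sets a severity threshold, and section 2.4 adds: "A positive test result or a presumed positive subject is not automatically a serious adverse event (SAE), unless an SAE criterion is met". The site enters one of two named coronavirus terms on the AE page, gives Adverse Event as the primary reason, and is told to "indicate the AE number in the" free-text field that specifies the reason. Subjects who leave because of COVID-19 "for reasons other than the subject testing positive OR being presumed positive with COVID-19" are coded as Other, with text that begins with COVID-19.

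SAP section 6.1 states: "Subject completion rate and reasons for discontinuation will be summarized for the Enrolled Sample by parent study treatment group and overall". It continues: "The above summaries will be repeated in subject subgroups as defined by gender", and also by age group, race, region and dementia severity. SAP section 9.1 codes events by system organ class (SOC) and preferred term (PT). Its item (f) is "TEAEs leading to discontinuation of the IMP", and (f) is repeated for events judged potentially related to study drug.

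Addendum section 2.5 leaves any COVID-19 effect on the analyses to the final SAP. The only COVID-19 analysis in the visible SAP is section 8.1, which summarizes the CMAI total score by visit type.

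**The concern.** Safety and tolerability is the trial's only objective, and no concurrent control shows how often subjects would stop anyway. Readers will take the share who stopped for an adverse event as a measure of tolerability. As section 6.1 is worded, its Adverse Event row would combine two kinds of case: an event that led the subject or investigator to stop, and a withdrawal the addendum requires even after a positive test without illness. If COVID-19 cases were common, the row could suggest poorer tolerability than the drug deserves, most visibly in small subgroup cells. The addendum points to the SAP for COVID-19 effects, and the visible SAP is silent on this one.

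**Working it through.** The plan states no figure to reproduce: the sample size is not based on power, and no rates of COVID-19 or AE discontinuation are given. The check is therefore a trace through the text, followed by a per-case bound.

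**1. Where each kind of COVID-19 withdrawal lands**

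| Situation | Withdrawal required? | Reason coded under Addendum 2.4 | Row in SAP 6.1 |
|---|---|---|---|
| Subject tests positive | Yes | Adverse Event, with AE number | Adverse Event |
| Subject presumed positive | Yes | Adverse Event, with AE number | Adverse Event |
| Caregiver positive, no replacement | Yes | Other (the subject is not positive) | Other |
| Quarantine, fear of infection | No | Other, with COVID-19 text | Other |

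Rule-driven withdrawals thus fall in two rows. Splitting only the Adverse Event row would leave the caregiver cases unseparated.

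**2. Entry into 9.1(f)**

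This is likely but inferred. Addendum 2.4 speaks of leaving the trial, whereas (f) needs an event that is treatment-emergent under the SAP definition and is recorded as leading to discontinuation of study drug. A subject who enters (f) carries a coronavirus term, which a display by PT would show. The SAP does not state the display level for (f).

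**3. Are the counts right, and can the cases be found?**

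Both hold. Protocol section 3.7.3.2 records withdrawal because of an AE as an AE, and the addendum follows that convention. The all-cause totals are correct as defined. The AE number ties each withdrawal to a coded term, so a split needs no new data. A COVID-19 event judged unrelated also drops out of the drug-related repeat of (f).

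**4. What one case can do**

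Protocol Appendix 4 (Amendment 2 background) gives an expected parent enrolment of roughly 255 or roughly 330. These serve only as approximate ceilings for the extension. The effect of one case, in percentage points, is 100/N, and each figure below is a lower bound because N is a maximum.

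| Denominator | Ceiling 330 | Ceiling 255 |
|---|---|---|
| Overall | 100/330 = 0.30 | 100/255 = 0.39 |
| Smallest of 3 parent groups | N ≤ 330/3 = 110; 100/110 = 0.91 | N ≤ 255/3 = 85; 100/85 = 1.18 |
| Smallest of 9 cells (3 groups × 3 subgroup levels) | N ≤ 36 (330/9 rounded down); 100/36 = 2.78 | N ≤ 28 (255/9 rounded down); 100/28 = 3.57 |

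The three groups are placebo, 2 mg and 3 mg; age and dementia severity each have three levels. Cases need not fall in the smallest cell. The same arithmetic applies to any reason code, so it says nothing about how many COVID-19 cases there are.

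**5. Illustration with assumed rates**

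Neither rate is in the documents. Take 5% stopping for other adverse events and 1%, 3% or 5% withdrawn under the rule. The Adverse Event row then shows 5 + 1 = 6%, 5 + 3 = 8% or 5 + 5 = 10%. COVID-19 makes up 1/6 = 17%, 3/8 = 38% or 5/10 = 50% of it. A sub-line would change the display but not the total.

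**The case for a change.** The best case for a change is that the addendum handed COVID-19 effects to the SAP, the visible SAP takes up only the CMAI, and prespecifying a split would avoid a choice made after the data are seen. Item (f) may show coronavirus terms, but section 6.1 describes no term-level display. The drug-related repeat of (f) is an imperfect substitute: it depends on the investigator's causality judgement and removes every other unrelated event as well. The cost would be a few rows.

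The silence is real, and a sub-line would help the reader. That does not make the plan deficient:

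- Section 6.1 is a disposition summary under study conduct and prescribes no row layout. Protocol 3.7.3.2 lists several other required withdrawals, so a reasons table is not built to separate required from elective stopping.
- There is little post-hoc freedom to guard against. The addendum fixed the terms and the link in advance, and the all-cause total stays the same however the row is shown.
- A total excluding COVID-19 would err low. Some subjects with serious infection would have stopped anyway, and those withdrawn can no longer stop for another event. In a safety-only trial that flatters the drug.
- Parts of the SAP were removed before review, so absence can be claimed only for the visible text. The 24-week safety analysis for subjects given brexpiprazole in the parent trial is also specified in a separate SAP that is not available here.

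**Conclusion.** No change to the plan is needed. Following it as written gives correct counts, and COVID-19 cases coded as adverse events can be separated from data already collected. What is missing is a display detail that the table shells can supply: COVID-19 sub-lines under both Adverse Event and Other in section 6.1, and item (f) shown by SOC and PT, with all-cause totals kept as the main figures. No total excluding COVID-19 is needed.

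The total effect cannot be sized from the documents. One case adds at least 0.30 to 0.39 points overall and at least 2.78 to 3.57 points in the smallest of nine subgroup cells, if the parent enrolment figures are a fair ceiling. The number of cases may be small: version 1 of the addendum never took effect, so subjects treated before a later version applied were not under the rule. The conclusion assumes that sites record the term and AE number as instructed. It takes no position on the withdrawal rule itself.

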2.5 Statistical Analyses

Any impact of COVID-19 on the planned statistical analyses for the trial will be described in the final statistical analysis plan.

2.6 Clinical Outcomes

To decrease variability, sites should attempt to standardize the method of administration for a scale for an individual subject and across all subjects in the trial. Assessments should be administered by the same qualified/trained rater who rated the subject previously; if this is not possible due to staff availability and/or technological limitations, discuss relevant information with previous raters to obtain clinical context (note that, per protocol, raters must be trained/qualified to conduct assessments in all cases). Raters

Protocol 331-201-00182

should conduct all assessments for that visit during the same remote session, where possible.

Please refer to *Virtual and Remote Visit Overview* and *Virtual Visit Instructions for Clinical Sites* for modification of administration methods for remote visits.

3 Trial Population

3.1 Inclusion Criteria

No changes are required to the inclusion criteria due to COVID-19. However, if there is a future restriction on face-to-face visits and virtual visits are mandated due to COVID-19, then hospitalized subjects who are currently enrolled in the parent Trial 331-14-213 where the investigator is also the subject's physician can rollover into the 331-201-00182 trial.

3.2 Exclusion Criteria

No changes are required to the exclusion criteria due to COVID-19.

4 Trial Procedures

If a virtual visit is conducted due to COVID-19 conditions, there are some assessments that can not be performed (eg, laboratory collections, electrocardiogram [ECG], Simpson Angus Scale [SAS]). Please refer to the *Virtual and Remote Visit Overview* and *Virtual Visit Instructions for Clinical Sites* for modification of administration methods for remote visits.

4.1 Safety Assessments

4.1.1 Vital Signs

Blood pressure, heart rate, weight, and temperature will all be measured as described in the protocol at the timepoints defined in this COVID-19 Addendum Schedule of Assessments ([Table 1.2-1](#)) with the following considerations:

- If blood pressure measurements cannot be collected for 2 consecutive visits, the medical monitor should be contacted for guidance.
- Subjects and caregivers will be asked to use their own collection device, if available, until devices can be provided.

Protocol 331-201-00182

- Where possible, site staff will remotely supervise the collection of measurements via video or guide by telephone, if video is not possible, on the appropriate visits.
- Subjects and caregivers will be instructed to be as consistent as possible regarding the time of day the measurement is taken, and to notify the site staff of the measurement results via telephone, or other means, on the appropriate visits.
- Site staff will be instructed to record the measurement in eSource, and if there are believed to be any errors, inconsistencies, or safety concerns with the reported home measurement, the medical monitor should be notified.
- Site staff will instruct the subjects to follow the procedures in the protocol for blood pressure and heart rate collection, but specify that the supine and standing positions for blood pressure are necessary, while the sitting position is less important. If sitting position is not collected, it should be documented as a COVID-19 protocol deviation (see [Section 2.3](#)).

4.1.2 Pregnancy

Pregnancy tests will be performed as described in the protocol at the timepoints defined in this COVID-19 Addendum Schedule of Assessments ([Table 1.2-1](#)) with the following changes:

- For planned visits that require a pregnancy test for women of childbearing potential (WOCBP), the site will provide the necessary tests and instructions so the test may be performed at home;
- Applicable subjects will perform a pregnancy test at the timepoints defined in [Table 1.2-1](#), ensuring a date- and time-stamped picture or video of the result is taken, followed by notification to the site staff of the results via telephone, or other means, on the appropriate visits. Subjects will also provide the site staff with the date- and time-stamped picture/video.
 - If negative, site to inform subject to proceed with dosing (if applicable).
 - If positive, the site must instruct the subject to immediately stop taking IMP (if applicable), and the site will refer to the Pregnancy section of the protocol for appropriate immediately reportable event reporting.

SAP 331-201-00182

List of Abbreviations and Definitions of Terms

Abbreviation	Definition
AAD	Agitation in Alzheimer's dementia
AE	Adverse event
AIMS	Abnormal Involuntary Movement Scale
ALT	Alanine aminotransferase
AST	Aspartate aminotransferase
BARS	Barnes Akathisia Rating Scale
BMI	Body mass index
CGI-S	Clinical Global Impression - Severity
CRF	Case Report Form
CMAI	Cohen-Mansfield Agitation Inventory
DBP	Diastolic blood pressure
ECG	Electrocardiogram
EPS	Extrapyramidal symptoms
ET	Early termination
FDA	(United States) Food and Drug Administration
HbA1c	Glycosylated hemoglobin
HDL	High density lipoprotein
IAF	Informed assent form
ICF	Informed consent form
ID	Identification
IMP	Investigational medicinal product
IRE	Immediately reportable event
LDL	Low density lipoprotein
LOCF	Last Observation Carried Forward
MedDRA	Medical Dictionary for Regulatory Activities
OPDC	Otsuka Pharmaceutical Development and Commercialization, Inc.
PE	Physical examination
QD	Once Daily
QTc	Corrected QT interval
QTcF	QT interval as corrected for heart rate by Fridericia's formula
SAE	Serious adverse event
SAS	Simpson Angus Scale
SAS®	Statistical Analysis System®
SAP	Statistical Analysis Plan
SCS	Summary of Clinical Safety
SOC	System Organ Class
TEAE	Treatment-emergent adverse event
ULN	Upper limit of normal

SAP 331-201-00182

1 Introduction

This statistical analysis plan (SAP) expands the statistical section of the protocol 331-201-00182 and documents in detail the statistical methodologies and data analysis algorithms and conventions to be applied to the analysis and reporting of the safety and tolerability data collected in the study. All amendments to the protocol have been taken into consideration in developing this SAP.

2 Study Objectives

Primary: To assess the long-term safety and tolerability of oral brexpiprazole as treatment in adult subjects with AAD.

3 Trial Details

